8.5. Analysis of the Secondary Endpoints

Descriptive statistical analyses will be performed on secondary endpoints. No inferential statistical analysis is planned for secondary endpoints.

Event rates such as mortality, secondary procedures, serious adverse events, conversion to open surgery, and aneurysm ruptures will be calculated in the same way as the MAE rate, specified in Table 2.

The survival from all-cause and aneurysm-related mortality over one year time or longer will be presented with the Kaplan-Meier survival curve and the associated Kaplan-Meier estimate will be calculated along with its standard error using the Greenwood method.

Imaging based event rate such as stent graft migration, aneurysm expansion, endoleaks, stent graft occlusions, and device deficiencies will be calculated in the way as specified in Table 3.

9. Additional Data Summaries / Supplemental Analyses

Descriptive data summaries will be provided for acute procedural observations and clinical utility measures.

10. Data Screening and Acceptance

Data management will be done according to Medtronic SOPs and the Data Management Plan for this clinical study. These documents will be made available upon request.

All collected data will be reviewed for completeness, correctness and consistency. In case of issues, queries will be sent to the investigator or designee to complete, correct or comment the data.

11. List of Planned Tables, Listings, and Figures

List of planned tables, listing, and figures for the analyses can be found in a separate table shell document.

12. Appendices

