Serious Adverse Device Effects (SADE), including Unanticipated Serious Adverse Device Effect (USADE):	Immediately (but no later than 3 calendar days) after the investigator first learns of the event or of new information in relation with an already reported event.
Serious Adverse Events (SAE)	Immediately (but no later than 3 calendar days) after the investigator first learns of the event or of new information in relation with an already reported event.
Adverse Device Effects (ADE)	Immediately (but no later than 3 calendar days) after the investigator first learns of the event.
All other AEs	Submit in a timely manner after the investigator first learns of the event.
Device Deficiency (with SAE potential)	Immediately (but no later than 3 calendar days) after the investigator first learns of the deficiency or of new information in relation with an already reported deficiency.
All other Device Deficiencies	Submit in a timely manner after the investigator first learns of the deficiency.

In addition, Investigators are obligated to report adverse events in accordance with the requirements of their IRB/EC and local regulations. The Sponsor is obligated to report adverse events and device deficiencies that occur during this trial to the Regulatory Authorities and IRB/EC as per local requirements. The applicable timeframes are described in the Endurant Evo Clinical Trial safetyplan.

F.6.5 Clinical Event Committee

A clinical event committee (CEC) will be established. The CEC is an independent committee made up of clinicians (interventional and non-interventional) with pertinent expertise who are not participants in the study and who do not have any other real or potential conflicts of interest. The CEC will meet periodically to review and adjudicate all major adverse events (except procedural blood loss), serious unanticipated adverse device effects, and all deaths that occur throughout the conduct of the clinical trial. A charter will be developed that will detail the criteria for selected

complications and clinical events that need to be adjudicated as well as the CEC composition, duties, procedures and adjudication rules and meeting frequency.

F.6.6 Emergency contact details in case of serious AEs

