In case of an immediately reportable Adverse Event the investigators can contact the Medtronic Study Manager. Contact details of Medtronic Study Management are given in the Investigational Site File. In case the investigator requires information in a medical emergency situation the investigator can contact the Medical Expert. Contact details of Medical Expert are given in the Investigational Site File.

F.7 Subject accountability

Every subject should be encouraged to remain in the study until they have completed the required follow up per the study protocol. If the subject discontinues prematurely from the study (e.g. withdrawal of the consent, lost to follow-up), the reason for discontinuation must be documented in the subject's hospital record and documented on the appropriate eCRF. Subjects will not be replaced in case of premature study discontinuation.

F.7.1 Criteria and procedures for exit from study

The Study Exit eCRF should be completed after the subject is exited from the study. A subject will be considered to have exited from the study for any of the following reasons:

- Subject completes follow-ups required by the investigational plan
- Subject dies
- Subject requests to be withdrawn
- Investigator requests that subject be withdrawn to protect the welfare of the subject
- Subject is lost to follow-up
- Subject has conversion to open repair
- Other(specify).

F.7.2 Study Withdrawal

Subjects may withdraw from the clinical study at any time and for any reason. If a subject decides to withdraw from the clinical study and agrees to provide the reason for withdrawal, the investigator will document the reason and indicate any relationship of the withdrawal to the study or products being investigated in the subject's hospital record in the subject's file. If discontinuation is because of safety or lack of effectiveness, the subject shall be asked to be followed as per their institution's standard of care outside the clinical study as further described in section F.7.6. In addition, subject withdrawal will be documented on the Study Exit eCRF.

F.7.3 Missed follow-up

A missed follow-up visit should be documented by the investigator and reported in the eCRF including the reason. If the date the subject is last known to be alive is obtained, this should be recorded on the Follow-up visit eCRF and the method of obtaining this date should be documented in the medical record.

F.7.4 Lost-to-follow-up

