After study termination relevant medical records may be made available by the investigational sites for the treating physician per local laws and regulations if needed for further subject treatment. As per local law and regulation the trial investigator may be contacted by the treating physician in case of questions related to the study device and treatment.

G.4 Study close out

Prior to completion of study close out, all data must be entered and approved in the EDC system. Medtronic and/or its designees will notify the site of the intention to close the study. Remote study close out visits may be performed. The intent of these visits will be to assure the investigator's regulatory files are up to date and complete and that any outstanding issues from previous visits have been resolved. Medtronic will notify and inform the site(s) that all requirements have been met with a study closure letter.

If required, EC/IRB and/or regulatory authority will be informed by Medtronic about the study close out.

H DATA ANALYSIS AND REPORTING

Any deviations from this section will be described and justified in the final clinical study report, as appropriate.

H.1 Analysis of clinical data

All endpoints will be analyzed descriptively. In general, qualitative parameters will be described by their distribution frequencies; quantitative parameters will be described by their mean, standard deviation, minimum, maximum, median, and number of subjects with assessable data.

The survival from all-cause mortality over one year time or longer will be described by the Kaplan-Meier survival curve and the associated Kaplan-Meier estimate will be calculated along with its standard error using the Greenwood method.

For events such as AEs, deaths and secondary procedures, that can occur or are observed at any time during the study, no time window will be applied. For such events, an event that occurs "within 1 month or 30 days" is an event that takes place between Days 0 to 30, inclusive. Similarly, an event that occurs "within 12 months or 365 days" is an event occurring between Day 0 to Day 365, inclusive. Date of event onset will be used to determine when the event occurred. Day 0 is referring to the day of index procedure.

For image-based assessments, such as stent-graft endoleak, patency, and other observations, the following time windows will be applied for by-visit data summaries:

Table H-1: Time Windows for Statistical Analyses

Study Visit	Target Day	Time Window

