PET	Polyethylene terephthalate
PMA	Premarket Approval
OD	Outer Diameter
SADE	Serious Adverse Device Effect
SAE	Serious Adverse Event
SOP	Standard operating procedure
USADE	Unanticipated Serious Adverse Device Effect
WBC	White Blood Cell

L.2 Definitions

Major Adverse Events (MAEs)	Definition
All-Cause Mortality	Death from any cause.
Bowel Ischemia	Bloody diarrhea with confirmation via colonoscopy of ischemia or the operative or postmortem demonstration of ischemic changes in the large or small intestine and requires surgical intervention.
Myocardial Infarction	Evidenced on 2 of the 3 following conditions: new clinical symptoms suggesting MI, changes on ECG consistent with MI, and elevated CK > 2 times the upper normal limit (per the normal ranges of the institution).
Paraplegia	Complete loss of motor function in the lower extremities occurring intra- or postoperatively and persisting >1 month.
Procedural Blood Loss \geq 1000 cc	A blood loss \geq 1000 cc occurring before the subject leaves the operating room.
Renal Failure	Failure of renal function requiring dialysis.
Respiratory Failure	Need for mechanical ventilation for > 24 hours postoperatively, or re-intubation for any reason.
Stroke	Development of a new neurological deficit that persists > 24 hours, or worsening of previous neurological symptoms that persist > 24 hours and classified as stroke by a physician.

Secondary Endpoints:	Definition
Aneurysm-Related Mortality	
Aneurysm-related mortality is defined as death from rupture of the abdominal aortic aneurysm or from any initial or secondary procedure intended to treat the AAA. If a death occurred within 30 days of any procedures intended to treat the AAA, then it is presumed to be aneurysm-related unless there is evidence to the contrary. Deaths that occurred after 30 days of any procedures intended to treat the AAA that are procedure-related should be aneurysm-related.
 
Ultimate adjudication of relatedness of death will be made by the Clinical Events Committee (CEC). Excluded are aneurysms in anatomic areas other than the targeted segment treated by the Endurant Evo AAA stent graft system.

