4.2. Subset

Subset analysis will be performed by-sex for the primary endpoints descriptively and reviewed for clinical significant difference.

5. Endpoints

Primary Safety Endpoint

The primary safety endpoint is defined as the proportion of subjects experiencing a MAE within 30 days post-implantation. MAEs include the occurrence of any of the following events:

- All-cause mortality
- Bowel ischemia
- Myocardial infarction
- Paraplegia
- Procedural blood loss ≥ 1000 cc
- Renal failure
- Respiratory failure
- Stroke

Primary Effectiveness Endpoint

Technical success at the index procedure (as assessed intra-operatively) is defined as successful delivery and deployment of the Endurant Evo AAA Stent graft system in the planned location and with no unintentional coverage of both internal iliac arteries or any visceral aortic branches and with successful removal of the delivery system.

Secondary Endpoints

- All cause-mortality within 30, 183, and 365 days
- Aneurysm-related mortality within 30, 183, and 365 days
- Secondary procedures to correct Type I and III endoleaks within 30, 183 and 365 days
- Secondary endovascular procedures within 30, 183 and 365 days
- Serious adverse events within 30, 183 and 365 days
- Aneurysm rupture within 30, 183 and 365 days
- Conversion to open surgery within 30, 183 and 365 days
- Major adverse events within 183 and 365 days
- Stent graft migration at 12-month follow-up visit (as compared to 1-month imaging)
- Aneurysm expansion > 5 mm at 12-month follow-up visit (as compared to 1-month imaging)
- All endoleaks based on imaging findings at 1- month, 6-month and 12-month visits
- Stent graft occlusion based on imaging findings through 6 months and 12 months
- Device deficiencies based on imaging findings through 6 months and 12- months

Secondary endpoints will be assessed at annual follow-up visits until 5 years post-implantation.

Additional Observations

The following acute procedural observations and clinical utility measures will be reported:

- Mean duration (min) of procedure (time between initial skin access to final skin closure)
- Proportion of subjects who underwent general/local/epidural/spinal anesthesia
- Proportion of subjects who underwent unilateral/bilateral percutaneous access
- Proportion of subjects requiring blood transfusions, excluding cell saver
- Mean volume (cc) of estimated blood loss
- Mean duration (min) of radiation exposure
- Radiation exposure (mGy)

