8.4. Analysis of the Primary Endpoints

For the primary endpoint, a one-sided 95% confidence interval based on binomial distribution will be constructed in addition to event count and frequency.

The analysis for the regulatory submission will take place when 40 subjects have been implanted with the study device for at least 30 days except that a subject expires early. Endpoints as defined in Section 5 will be analyzed for these 40 ITT subjects.

MAE Rate Calculation:

All MAEs will be adjudicated by the Clinical Event Committee (CEC) per protocol except for the procedural blood loss ≥ 1000 cc, which will be site reported at the index procedure. MAE rate will be calculated as follows (Table 2):

Table 2: MAE Rate Calculation:

MAE rate = $m/(m + k)$	Within 30 Days	Within 183 Days	Within 365 Days
$m = \text{No. of Subjects Who Had MAE(s)}$	No. of subjects who had at least one MAE with onset day from Day 0 to Day 30, inclusive.	No. of subjects who had at least one MAE with onset day from Day 31 to Day 183, inclusive.	No. of subjects who had at least one MAE with onset day from Day 184 to Day 365, inclusive.
$k = \text{No. of Subjects Who Had No MAE}$	No. of subjects who have been in study for at least 1 day and without an MAE.	No. of subjects who have been in study for at least 91 days and without an MAE.	No. of subjects who have been in study for at least 305 days and without an MAE.

If a subject is early terminated from the study, the last day that the subject has been seen will be the duration in study, which can be the day of last follow-up, last imaging taken, an AE reported, or withdrawal from the study. If a subject is still in the study, the duration in study will be the time from index procedure to the cut off day that the database is locked or data snapshot is taken.

Imaging based Event Rate Calculation:

Imaging assessment will be performed by site as well as the core lab. Assessments from the core lab will be analyzed separately from those by site. Imaging based event rate will be calculated using statistical analysis windows as follows (Table 3):

Table 3: Imaging based Event Rate Calculation:

Event rate = m/n	At 1 Month	At 6 Months	At 12 Months
$m = \text{No. of Subjects Who Had Event(s)}$	No. of subjects who had an event with scan day within the 1-month window.	No. of subjects who had an event with scan day within the 6-month window.	No. of subjects who had an event with scan day within the 12-month window.

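### Kaplan-Meier for aneurysm-related mortality can overstate the actual risk of aneurysm-related death, because other-cause deaths enter the curve as censored; a cumulative incidence estimate avoids this (minor point)

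*SAP*

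**What the plan says.** SAP 8.5 plans: "The survival from all-cause and aneurysm-related mortality over one year time or longer will be presented with the Kaplan-Meier survival curve", with a Greenwood standard error. Protocol H.1 is narrower: "The survival from all-cause mortality over one year time or longer will be described by the Kaplan-Meier survival curve". SAP 8.1 is likewise limited to all-cause mortality, so only SAP 8.5 extends the method to a cause-specific endpoint.

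Protocol Appendix L.2 defines the event as "death from rupture of the abdominal aortic aneurysm or from any initial or secondary procedure intended to treat the AAA". It also presumes that a death within 30 days of such a procedure is aneurysm-related unless evidence points the other way. Under Protocol F.6.5 the Clinical Event Committee (CEC) adjudicates "all deaths that occur throughout the conduct of the clinical trial", so other-cause deaths will be identified.

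Death of any cause ends participation (Protocol F.7.1). SAP 8.4 gives a rule for time in study under the MAE rate: "If a subject is early terminated from the study, the last day that the subject has been seen will be the duration in study". Neither document has a separate rule for other-cause death in the aneurysm-related curve, and neither mentions competing risks or cumulative incidence. On the horizon, SAP section 5 says: "Secondary endpoints will be assessed at annual follow-up visits until 5 years post-implantation".

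**The concern.** A subject who dies of another cause can no longer die of the aneurysm. Kaplan-Meier handles a censored subject as someone who remains at risk and will fare like those still under observation. Applied to aneurysm-related death, one minus the curve therefore describes a setting in which no one dies of anything else. That is a legitimate net quantity if censoring is independent, but it is not the proportion of treated subjects who die of their aneurysm or its treatment. Readers of a device report usually want the latter.

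The gap grows with other-cause mortality and with the lateness of aneurysm-related deaths. Follow-up runs to 5 years in an aneurysm population, and Protocol J.3 reports stent fractures and detachment, so late aneurysm-related deaths are conceivable, although the documents report none. At stake is the accuracy of one descriptive secondary estimate.

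**Working it through.** **The plan's own figures.** The documents give no rate for aneurysm-related or other-cause mortality, so there is no figure on this point to reproduce. The one precision figure, a margin below 10% in Protocol C.7 and SAP 3.2, concerns 30-day MAEs. It reproduces (exact one-sided 95% upper limit for 2/40 is 14.92%, a margin of 9.92 points) but has no bearing here.

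**Inputs from the documents.** 69 subjects enrolled (Protocol C.5); 5 years of follow-up (SAP section 5); Kaplan-Meier with Greenwood standard error (SAP 8.5). All mortality rates below are assumptions.

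**Check 1: constant hazards.** Let a be the yearly aneurysm-related hazard and o the yearly other-cause hazard.

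- One minus Kaplan-Meier at 5 years: 1 - exp(-5a)
- Cumulative incidence at 5 years: a/(a+o) × [1 - exp(-5(a+o))]

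| a | o | 1-KM | Cumulative incidence | Excess (points) | Ratio |
|---|---|---|---|---|---|
| 0.005 | 0.06 | 2.47% | 2.13% | 0.33 | 1.16 |
| 0.005 | 0.10 | 2.47% | 1.945% | 0.52 | 1.27 |
| 0.01 | 0.06 | 4.88% | 4.22% | 0.66 | 1.16 |
| 0.01 | 0.10 | 4.88% | 3.846% | 1.03 | 1.27 |

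These hazards imply other-cause mortality of about 25-39% at 5 years, from o/(a+o) × [1 - exp(-5(a+o))].

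**Check 2: a wider range of other-cause mortality.** Fix the 5-year cumulative incidences A (aneurysm-related) and O (other-cause). Then a + o = -ln(1-A-O)/5 and a = (a+o) × A/(A+O). For A = 3%:

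| O | 1-KM | Ratio |
|---|---|---|
| 10% | 3.16% | 1.05 |
| 20% | 3.35% | 1.12 |
| 30% | 3.58% | 1.19 |
| 40% | 3.85% | 1.28 |

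If every aneurysm-related death comes after every other-cause death, the ratio reaches its ceiling of 1/(1-O), which is 1.11 to 1.67 over the same range.

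**Check 3: worked data sets with 69 subjects.** Two aneurysm-related deaths, 7 to 28 other-cause deaths spread evenly over 5 years, and complete follow-up otherwise. The cumulative incidence is 2/69 = 2.90% throughout.

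| Timing of the two aneurysm-related deaths | 1-KM | Excess (points) | Greenwood SE (points) |
|---|---|---|---|
| Both within 30 days | 2.90% | 0 | 2.0 |
| Years 1.5 and 3.5 | 3.06-3.65% | 0.2-0.75 | 2.1-2.55 |
| Years 4 and 4.8 | 3.15-4.51% | 0.25-1.6 | 2.2-3.1 |

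The most extreme case can be followed by hand. With 28 other-cause deaths, 22 fall before year 4 and 27 before year 4.8. The risk sets are 69 - 22 = 47 and 69 - 27 - 1 = 41.

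- Kaplan-Meier: 1 - (46/47)(40/41) = 4.51%
- Aalen-Johansen: (47/69)(1/47) + (41/69)(1/41) = 2/69 = 2.90%

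**Does Table 2 already supply the risk?** No. SAP 8.5 also applies the Table 2 rates to mortality, but its columns stop at day 365. In the later columns an event-free subject counts in the denominator only after 91 or 305 days in study, so an earlier other-cause death drops out of it.

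**The case against.** The strongest objection is materiality. An excess of 0.3-1.0 points is 0.2-0.7 of one subject in 69, and at the assumed hazards only about one to three aneurysm-related deaths are expected in all (69 × 1.9% = 1.3; 69 × 4.2% = 2.9). The planned standard error already shows more uncertainty than that. Secondary endpoints are descriptive, with no test, threshold or comparator. This stands and sets the severity.

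Second, SAP 8.5 promises a survival curve from one year onward. It names no 5-year estimate and does not say that one minus the curve will be called the actual risk. The censoring rule is inferred, and the table shells are a separate document. This stands in part: the curve misleads only when read as absolute risk, but nothing in the SAP warns against that reading.

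Third, the 30-day presumption in Appendix L.2 pulls events toward the index procedure, and with all events there the gap is nil. It also applies after any later aneurysm procedure, so it does not rule out late events.

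Fourth, the higher other-cause rates are uncertain. Protocol B.1 describes people who typically develop these aneurysms, whereas entry requires ASA class I-III and excludes life expectancy of one year or less, recent infarction or stroke, creatinine above 2.00 mg/dl and dialysis. This stands, which is why the 10% case is shown.

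A reader might infer that the plan is bound to overstate the 5-year risk, or that the flaw hides harm. The documents support neither. The direction depends on the timing of deaths, and any error makes the device look worse.

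**Conclusion.** The point holds as a minor accuracy point. For a cause-specific endpoint, one minus Kaplan-Meier is never below the cumulative incidence and exceeds it when an aneurysm-related death follows an other-cause death. It is a biased estimate only if taken as the actual risk of aneurysm-related death.

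The size rests wholly on assumed rates: a ratio of about 1.05 with 10% other-cause mortality at 5 years, and 1.16-1.27 at other-cause hazards of 6-10% a year. In the 69-subject examples the excess is 0 to 1.6 points, always within one standard error. The small sample limits the consequence but does not make the estimator answer the question a reader will ask.

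It would go too far to infer that the all-cause curve, the primary endpoints or the 40-subject regulatory analysis are affected. All-cause death has no competing event, and the primary endpoints are assessed at the index procedure and at 30 days as simple proportions.

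**What to change.** Amend the mortality sentence in SAP 8.5:

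- Keep Kaplan-Meier with Greenwood standard error for all-cause mortality.
- For aneurysm-related mortality, report the Aalen-Johansen cumulative incidence with its own standard error. Count CEC-adjudicated aneurysm-related death as the event and any other death as the competing event. Withdrawal, loss to follow-up and end of follow-up remain censoring.
- If a Kaplan-Meier curve is wanted for comparison with other device reports, keep it as a supplement labelled as cause-specific with other-cause deaths censored.

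The cost is one SAP sentence, a matching line in the table shells and a standard routine. No new data are needed, since adjudication of every death is already planned.

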The study population will include those subjects who are appropriate candidates for endovascular repair of infrarenal abdominal aortic or aortoiliac aneurysms, and who meet the Inclusion/Exclusion criteria (defined in Section D).

C.5 Study design

The Endurant Evo International Clinical Trial is a prospective multi-center, pre-market, non-randomized, single-arm trial. The trial is designed to assess the clinical safety and performance of the Endurant Evo AAA stent graft system. A sample of 40 subjects will be enrolled consecutively and evaluated at the 30-day primary safety endpoint. Data from these 40 subjects will be analyzed and used to support regulatory approval. All subjects enrolled will continue to be followed under this investigational protocol beyond the 30-day primary endpoint until 5 years post-implantation.

Given the DDs with SAE potential that have occurred within the Endurant Evo trials (transition stent fracture, partial suprarenal stent detachment, and suprarenal stent fracture), enrollment was terminated with a total enrollment of 69 subjects.

Subjects will have required follow-up evaluations at the following time points:

- 1 month following the index procedure
- 6 months following the index procedure
- 12 months following the index procedure
- Annually thereafter, until 5 years post index procedure

Given the DDs with SAE potential that have occurred within the Endurant Evo trials, the Data Monitoring Committee (DMC) has made additional imaging surveillance recommendations, beyond the required follow-up in the protocol. The additional imaging surveillance recommendations are provided, under separate cover, in the most recent DMC Surveillance and Management letter that has been provided to each investigational site.

In addition to the 40 subjects enrolled to support regulatory approval, approximately 30 additional subjects may be enrolled to support geography-specific regulatory requirements. For these subjects, all inclusion/exclusion criteria, study methods, follow-up schedule and data-collected will be identical to the first 40 subjects enrolled.

Number of devices being used within this trial

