3.2. Sample Size Consideration

A sample of 40 subjects will be treated and analyzed to support regulatory approval. The sample size of 40 subjects is considered adequate to assess the primary safety endpoint, which is defined as the proportion of subjects experiencing a MAE within 30 days post-implantation.

Considering the reported MAE rate from the ENGAGE Post-Approval Study (PAS), which evaluated the long-term safety and effectiveness of the Endurant Stent graft system in 328 subjects¹, it is estimated that 2 of 40 (5%) subjects treated with Endurant Evo AAA stent graft system will experience a MAE. The precision of this assumed 5% point estimate can be assessed by calculating the difference from the 1-sided 95% upper confidence limit. This difference, or margin of error, is calculated to be < 10% for the Endurant Evo International Clinical Trial and is therefore considered adequate to assess the primary safety endpoint^{2,3}.

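### SAP 8.5 gives aneurysm-related survival only a Greenwood standard error, which is exactly 0 if no such death occurs and has no interval or zero-event rule behind it

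*SAP*

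**What the plan says.** SAP 8.5 covers two mortality endpoints: "The survival from all-cause and aneurysm-related mortality over one year time or longer will be presented with the Kaplan-Meier survival curve". The precision measure follows in the same sentence: "the associated Kaplan-Meier estimate will be calculated along with its standard error using the Greenwood method". SAP 8.1 and Protocol H.1 plan the same measure for all-cause mortality alone; Protocol H.1 reads "The survival from all-cause mortality over one year time or longer will be described by the Kaplan-Meier survival curve".

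SAP 8.5 also states: "No inferential statistical analysis is planned for secondary endpoints". Crude mortality is handled separately, by the formula set out for MAEs in Table 2 of SAP 8.4: "Event rates such as mortality, secondary procedures, serious adverse events, conversion to open surgery, and aneurysm ruptures will be calculated in the same way". That table has columns to Day 30, Day 183 and Day 365 and no interval.

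The one interval in the plan belongs to the primary endpoint (SAP 8.4): "For the primary endpoint, a one-sided 95% confidence interval based on binomial distribution will be constructed in addition to event count and frequency".

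Two sample sizes matter. For the submission, SAP 3.2 says "A sample of 40 subjects will be treated and analyzed to support regulatory approval". For the whole trial, Protocol C.5 reports that "enrollment was terminated with a total enrollment of 69 subjects", with follow-up to 5 years.

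**The concern.** The plan names an error measure for late aneurysm-related survival, and that measure breaks down in a quite possible data set. Greenwood's variance is a sum over death times. With no death the sum is empty and the standard error is 0, whatever the number followed. After the last death the variance term stops growing, however few subjects remain under observation.

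Aneurysm-related death may well be rare, and the trial has at most 69 subjects. A 5-year result of 100% with standard error 0% would read as certainty. The trial stopped enrolling because of stent fractures and detachments, and Protocol J.3 describes risks worse than those of the predicate device. In that setting a reader should see how large an aneurysm-related risk the data leave open.

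**Working it through.** **Inputs from the documents.** n = 40 (SAP 3.2) and n = 69 (Protocol C.5); 5 years of follow-up; planning figure of 2 MAEs in 40 with a margin below 10 points (SAP 3.2). The documents give no expected aneurysm-related mortality and no loss to follow-up. Risks of 1 to 5%, other-cause death at 6% per year, and 30 subjects still observed are therefore assumptions.

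**1. The plan's own precision figure.** The exact one-sided 95% upper limit for 2/40 is 14.9%. The margin is 14.9 − 5.0 = 9.9 points, so the stated figure reproduces. There is no comparable figure for mortality.

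**2. No deaths.** Greenwood: SE = S × √Σ d/[r(r − d)], with d deaths among r at risk at each death time. With no deaths, S = 1, the sum is 0 and SE = 0. The exact one-sided 95% upper limit for the risk is 1 − 0.05^(1/n):

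| Subjects observed | Greenwood SE | Exact upper limit |
|---|---|---|
| 69 | 0 | 4.2% |
| 40 | 0 | 7.2% |
| 30 (assumed) | 0 | 9.5% |

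**3. How likely that is.** Take a constant aneurysm-related hazard h = −ln(1 − p)/5 and other-cause hazard o = 0.06 per year, with no other loss. One subject's chance of an observed aneurysm-related death by 5 years is q = [h/(h + o)] × [1 − e^(−5(h + o))]. The chance of none in 69 is (1 − q)^69.

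| True 5-year risk p (assumed) | q | P(no death), n = 69 | Same, no other-cause death: (1 − p)^69 |
|---|---|---|---|
| 1% | 0.86% | 55% | 50% |
| 2% | 1.73% | 30% | 25% |
| 3% | 2.59% | 16% | 12% |
| 5% | 4.33% | 5% | 3% |

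**4. One death in 69, no censoring.** S = 68/69 = 98.55%. The variance sum is V = 1/(69 × 68) = 0.000213, √V = 0.01460, and SE = 0.9855 × 0.01460 = 1.44%. The binomial SE √[p(1 − p)/n] is also 1.44%.
- Symmetric: 98.55 ± 1.96 × 1.44 gives 95.7 to 101.4%.
- Log(-log): s = √V/|ln S| = 0.01460/0.01460 = 1.00, and the limits S^exp(±1.96 s) are 90.2 and 99.8%.

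The symmetric interval allows a risk up to 4.3%; the log(-log) interval allows 9.8%. With two deaths in 69 (SE 2.02%), the symmetric interval is 93.1 to 101.1% and the log(-log) interval 88.9 to 99.3%.

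**5. Where symmetric-interval coverage is lost.** Simulating the model of step 3 with n = 69, estimate ± 1.96 SE covers the true 5-year value in 45, 70, 83 and 86% of trials at risks of 1, 2, 3 and 5%. Among trials with at least one death, coverage is at least 99.7% at risks of 1 to 3% and about 90% at 5%. Nearly all of the loss therefore comes from the zero-death trials of step 3. A log(-log) interval, with the exact limit at zero deaths, covers 96 to 98%.

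**6. All-cause survival.** At an assumed 5-year all-cause risk of 30%, the symmetric interval covers about 93% with either 69 or 40 subjects.

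**The case against.** The strongest reply is that the plan is openly descriptive. It proposes no ± 1.96 SE interval, tests nothing on secondary endpoints, and attaches no decision to this standard error. Coverage figures therefore judge an interval that the plan does not contain. This stands in part: they show what happens if a reader forms the usual interval, and they are not an error in a planned analysis. It does not rescue the zero, because a descriptive standard error is still meant to describe uncertainty.

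A second reply is that crude counts let a reader derive a bound. That helps within the first year, but Table 2 stops at Day 365 and gives no fallback for years 2 to 5. Numbers at risk or intervals may be in the separate table shells, which were not available.

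Three stronger readings are tempting and are not supported:
- A reader might infer that the Greenwood SE is far too small with one or two deaths. Without censoring it equals the ordinary binomial SE (step 4). With heavy censoring it can be low, but moderately: for one early death in 40 with an assumed 20 still at risk, a Peto-type SE is 0.975 × √(0.025/20) = 3.4%, against 2.5%.
- A reader might infer that all mortality results are affected. SAP 8.1 and Protocol H.1 concern all-cause mortality, where deaths accumulate and the method performs adequately (step 6).
- A reader might infer that late mortality is the trial's main reassurance about the device. No section says so; stent failures are followed through imaging, core-lab review and device-deficiency reporting.

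The 40-subject submission analysis is triggered at 30 days (SAP 8.4), so n = 40 is a marginal case for late survival; 69 is the relevant number.

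**Conclusion.** The point holds for aneurysm-related survival in SAP 8.5. The only planned error measure is exactly 0 when no such death has occurred, although the data would leave open a risk of 4.2% (69 followed) to 9.5% (30 observed, assumed). The chance of that output with 69 subjects runs from about 55% at a true 5-year risk of 1% to about 5% at a risk of 5%. These chances rest on assumed risks, constant hazards, other-cause death of 6% per year and no other loss. The zero itself and the exact limits for a given number observed depend on none of the assumed rates.

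With one or two deaths the weakness is confined to a symmetric interval built from the standard error, which is short on the risk side and passes 100% survival. The primary endpoint, the sample size and all-cause survival are not materially affected. This is a reporting defect worth correcting before the late results are produced.

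**What to change.** In SAP 8.5, replace the standard-error clause with wording such as: Kaplan-Meier aneurysm-related survival will be reported with a two-sided 95% confidence interval on the log(-log) scale (Greenwood variance) and the number at risk at each reported time. If no event has occurred by that time, the one-sided 95% exact binomial upper limit for the event risk will be given instead, based on the number of subjects observed to that time.

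The one-sided 95% level matches the primary endpoint and should be stated, because a two-sided limit is larger (11.6% against 9.5% with 30 observed). Counting only subjects observed to the time point ignores partial follow-up, so this limit errs on the wide side. The same interval may be used for all-cause survival in SAP 8.1 and Protocol H.1 for consistency, but the case there is weaker.

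The cost is a sentence of SAP wording, matching table shells and a standard software option. No data are added and the analysis stays descriptive. The price is a wider, less flattering statement of uncertainty.
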